5.0 STATISTICAL METHODS

Primary Endpoint and Sample Size Adjustment

Hypothesis Testing

The study's primary endpoint has been previously defined. The associated statistical hypothesis is that the resulting event-free rate at 36 months is greater than the Performance Goal (PG), which is adapted from RESILIENT 3-year data on freedom from TLR for PTA subjects.

The null and alternative hypotheses for the primary endpoint are:

H ₀ :	$\pi_t \leq \pi_{pg}$

Ha: $\pi_t > \pi_{pg}$

where π_t is the event-free rate in subjects treated with an EverFlex device and π_{pg} is the PG of 35%.

Analysis of this endpoint will be carried out by Kaplan-Meier methods. The point estimate of the event-free rate at 36 months (1095 days) from the date of the index procedure will be computed along with its one-sided 97.5% lower confidence bound. If the lower bound is greater than 35%, it will be declared that the PG and the corresponding primary study objective have been met.

Justification of Performance Goal

The structure of the composite endpoint is derived from a 12-month composite endpoint described by VIVA Physicians Inc. (VPI) as part of their development of safety and effectiveness Performance Goals (PG) for the use of bare nitinol stents in the treatment of femoropopliteal lesions.^{19, 20} The VPI 12-month composite was defined as acute death, index limb amputation and target vessel revascularization (TVR) through 12-months. This composite event rate in the studies reviewed was 30.5% at 12 months (Table 8). However, there were no long-term follow-up to 3 years reported.

	Company A	Company B	Company C	Combined
	(n=29)	(n=24)	(n=63)	(n=116)
12 month Composite (acute death, 12m TVR, 12m amputation	38.5% (10/26)	33.3% (6/18)	25.5% (13/51)	30.5% (20/95)

Table 8: PTA Performance	e Goals – Safety Data
--------------------------	-----------------------

Recently, 3-year data on freedom from TLR was presented on the PTA arm of the RESILIENT study.²¹ The reported event-free rate at 3 years among RESILIENT subjects randomized to PTA treatment was 41.8%, a value which is adjusted as follows to account for longer lesions enrolled in DURABILITY II.

The statistical model employed is a Cox regression on the outcome of freedom from TLR applied to DURABILITY II data. Lesion length (in mm) as measured by the core laboratory was the predictor of outcome, resulting in a point estimate of 0.01543 for the logarithm of the hazard ratio, and therefore a hazard ratio of $e^{0.01543}$ =1.0155 per mm of lesion length (with longer lesions associated with lower freedom-from-TLR rates).

As the mean lesion length in RESILIENT was 68 mm versus 89 mm in DURABILITY II, the resulting adjusted event-free rate can be obtained using a formula analogous to adjusting with odds ratios:

 $\pi_{pg}/(1-\pi_{pg}) = (0.418/(1-0.418))^{*}1.0155^{(89-68)}$

Solving this equation gives $\pi_{pg} = 0.342$, which is rounded up to give the PG of 35%. Note that this PG is conservative in that it (1) does not attempt to account for any other systematic differences between RESILIENT and DURABILITY II and (2) does not explicitly account for the other elements of the composite endpoint (since these were not presented for RESILIENT), which if included would lower the expected freedom-from-event rate below that seen for TLR alone.

Potential Outcomes

Table 9 summarizes approximate outcomes under potential results for freedom from event, using binomial estimation. Note that the actual analysis will be conducted using time-to-event methods and is subject to currently unknown censoring times, and that therefore the actual success criteria will vary slightly from those noted below.

Table 9: Approximation to Possible Outcomes and Corresponding 97.5% LowerConfidence Bound

Primary Endpoint (PG=35%)			
Sample Size	Count of subjects with freedom from event	36-Month Freedom From Event Rate	97.5% lower confidence bound
108	48	44.4%	35.1%
108	49	45.4%	36.0%
108	50	46.3%	36.9%
108	51	47.2%	37.8%

Sample Size and Power

The required sample size for evaluating the primary endpoint can be approximated using the normal method for testing a single proportion (as above, under Kaplan-Meier methods the actual power will vary slightly from this calculation):

$$n = \frac{(\pi_{pg} \times (1 - \pi_{pg})) \times (Z_{1 - \alpha} + Z_{1 - \beta} \sqrt{\pi_t (1 - \pi_t) / (\pi_{pg} (1 - \pi_{pg})))^2}}{(\pi_t - \pi_{pg})^2}$$

Where,

- Type I error (α) = 0.025 (one-sided)
- Statistical power $(1 \beta) = 90\%$
- Z is the standard normal deviate for $\alpha = 0.025$ and $\beta = 0.10$.
- π_t is estimated freedom-from-event at 36 months
- π_{pg} is the PG

Using this approximation with $\pi_t = 0.55$ (estimated from current DURABILITY II data), $\pi_{pg} = 0.35$ (the *a priori* performance goal), $Z_{1-\alpha} = 1.96$ and $Z_{1-\beta} = 1.28$ gives a sample size of 62. Allowing for approximately 30% of subjects lacking a 3-year follow-up visit, the needed sample size under this approximation for 90% power is a minimum of 89.

An additional sample size requirement is based on the secondary endpoint of freedom from stent fracture at 1 year. In DURABILITY I and DURABILITY II, 1-year stent fracture rates of 8.1% (n=151) and 0.4% (n=287), respectively, were observed. The pooled fracture rate of these two studies is 3.0% (13/438), around which a confidence interval of specified width is desired. The desired precision is 7.2% (half-width of 3.6%); we therefore find a 95% two-sided normal confidence interval with upper bound 3.0% + 3.6% = 6.6%, and extract the relevant sample size.

Sample Size for Freedom from Stent Fracture			
Sample Size	Count of subjects with event	Event Rate	97.5% upper confidence bound (95% two-sided)
95	3	3.16%	6.67%
96	3	3.13%	6.61%
97	3	3.09%	6.54%
98	3	3.06%	6.47%

	Table 10:	Sample Size	e Freedom from	Stent Fracture
--	-----------	-------------	----------------	----------------

From the above table, the required sample size at 1 year is 97 subjects. Considering a 10% rate of attrition, a minimum of 108 subjects are needed, which is larger than the sample size

of 89 calculated for the primary endpoint. The enrolled sample size is therefore 108. Please note that multiple stents are allowed in each subject in the study. The stent fracture endpoint will be analyzed on stent level. To be conservative, sample size calculation is performed on subject level. Therefore more stents than the above assumption may be included in the analysis.

Data Analysis Plan

All statistical analyses will be performed using Statistical Analysis System (SAS) for Windows (version 9.2 or above, SAS Institute Inc. Cary, N.C.) or other widely accepted statistical or graphical software. In general, data for all study subjects combined will be presented. Individual data will be presented in subject listings.

Descriptive statistics will be used to present the data and to summarize the results. Discrete variables will be presented using frequency distributions and cross-tabulations. Continuous variables will be summarized by presenting the number of observations (N), mean, standard deviation, median, minimum, and maximum values.

For adverse event reporting, the primary analysis will be based on subject counts, not event counts. A subject with more than one event will be counted only once toward the event rate based on the total number of subjects with adverse events.

Unless otherwise specified, statistical significance will be declared when p<0.05 for twosided tests and p<0.025 for one-sided tests such as the primary endpoint.

Analysis of Secondary Endpoints

For secondary endpoints, descriptive statistics will be provided. No formal statistical hypothesis testing will be performed. Categorical variables will be analyzed using frequency tabulation and event rate. For continuous variables, analysis will include mean, median, standard deviation, and ranges. Time-to-event variables including the primary endpoint and the secondary endpoint of freedom from stent fracture will be analyzed using survival analysis and reported at 1 year (365 days), 2 years (730 days) and 3 years (1095 days), with Kaplan-Meier plots provided.

Analysis of Ability to Pool Data Across Investigational Sites

This is a multi-center clinical study, with standardization of subject enrollment, data entry and adverse event reporting. All investigational sites will follow the requirements of a common protocol, data collection procedures and forms. To present the data from this clinical study in a summary form, a comparison across all sites will be completed to determine if the generated data could be pooled. The following variables will be completed to assess the appropriateness of pooling data from across all sites:

- Baseline demographics such as age and gender
- Lesion characteristics such as lesion length and percent stenosis

The distributions of the above variables across the sites will be tabulated. To detect site differences, t-tests or Wilcoxon's rank-sum test will be used for continuous variables and Fisher's exact test for categorical variables.

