8. Improvement in Ankle-Brachial Index at 1 Year Defined as an increase in the ankle-brachial index (ABI) compared to baseline in subjects with compressible arteries and baseline ABI < 0.9.
9. Walking Improvement at 1 Year Defined as an increase in Walking Impairment Questionnaire score in

	subjects who did not have iliac disease treated at the time of the index procedure compared to baseline.				
	10. Adverse Event Rates Defined as the rate of adverse events that occur during the course of the study; event and subject counts as well as proportions of subjects with events categorized by type will be reported. Note that adverse events are captured at each study assessment. Counts and rates of all-cause mortality will be reported both as part of the overall adverse event profile as above, and separately as a specific outcome.				
Timeline	Date of First IRB Approval: Q3 2012				
	Date of Last IRB Approval: Q2 2014				
	Date of First Subject Enrolled: 14 January 2013				
	Estimated Date of Last Subject Enrolled: Q1 2015				
	Estimated Enrollment Rate: 0.33 subjects/site/month				
	Date of 6 Month Report: 15 August 2012				
	Date of 12-Month Report: 27 February 2013				
	Date of 18-Month Report: 29 August 2013				
	Date of 2-Year Report: 19 February 2014				
	Estimated Study Completion Date: Q4 2018				
	Estimated Date of Final Report Submission: Q4 2018				

TABLE OF CONTENTS

1.0	INTRODUCTION	9
Pu	pose9	
De	- vice Name	
In	ication for use9	
St	dy Overview9	
D	ration of the Investigation9	
N	mber of Sites and Subjects9	
2.0	DEVICE DESCRIPTION 10	D
E١	erFlex Device Sizes	
Еv	erFlex Device Components and Principles of Operation10	
3.0	BACKGROUND AND SIGNIFICANCE 10	Ð
Di	ease Overview	
Su	nmary of Clinical Trials in the SFA with the EverFlex Stent	
Cl	nical Experience with the EverFlex Stent	
4.0	METHODOLOGY	2
St	dy Design	
St	dy Objective and Primary Endpoints	
Su	pject Selection Criteria	
O	erview of Study Conduct	
Ba	seline Requirements	
Pr	cedure Requirements	
М	dical Anticoagulant/Antiplatelet Therapy22	
Fc	low-Up Requirements	
Τe	mination of Participation25	
De	viations to the Investigation	
De	vice Malfunctions	
A	verse Events	
De	aths 28	
Co	e Laboratory Requirements	
Cl	nical Events Committee	
Са	e Report Forms	

5.0	STATISTICAL METHODS	
Prin	mary Endpoint and Sample Size Adjustment	30
Hyp	pothesis Testing	
Just	tification of Performance Goal	
Pot	ential Outcomes	
San	nple Size and Power	
Dat	ta Analysis Plan	
6.0	RISK/BENEFIT ANALYSIS	

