DURABILITY II enrolled 287 subjects at 44 investigational sites in both the United States and Europe. A total of 303 stents were implanted: single stents in 95% (272/287), and 5.0% (15/287) received multiple stents. The mean age of subjects was 68 years, with 66% male. Co-morbidities include hypertension (88%), hyperlipidemia (86%), and diabetes (43%). The mean lesion length measured by core laboratory was 89.1 mm. The mean normal-to-normal lesion length measured by sites was 109.6 mm. Deployment of the stent at the intended treatment site was achieved in 99.3% of subjects. No major adverse events occurred at 30 days. Primary duplex ultrasound stent patency at 1 year in all subjects including single-stent and multi-stent implants was 67.7%. The primary patency by Kaplan Meier estimate at 1 year was 77.2%. At 2 and 3 years, primary patency was 66.1% and 60.0%, respectively. The mean Rutherford classification fell from 2.8 ± 0.6 (range 2-5) at baseline to 0.6 ± 1.1 (range 0-5) at 1 year. The mean ankle-brachial index rose from 0.65 ± 0.15 (range 0.06-0.89) at baseline to 0.89 ± 0.20 (range 0.25-1.77), 0.88 ± 0.19 (range 0.26, 1.27) and 0.89 ± 0.19 (range 0.31, 1.33) at 1, 2, and 3 years, respectively. The 1-year stent fracture rate was 0.4%; and was 0.9% at 2 and 3 years, respectively.

DURABILITY 200

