$$n = \frac{(\pi_{pg} \times (1 - \pi_{pg})) \times (Z_{1-\alpha} + Z_{1-\beta} \sqrt{\pi_t(1 - \pi_t) / (\pi_{pg}(1 - \pi_{pg}))})^2}{(\pi_t - \pi_{pg})^2}$$

Where,

- Type I error (α) = 0.025 (one-sided)
- Statistical power ($1 - \beta$) = 90%
- Z is the standard normal deviate for $\alpha = 0.025$ and $\beta = 0.10$.
- π_t is estimated freedom-from-event at 36 months
- π_{pg} is the PG

Using this approximation with $\pi_t = 0.55$ (estimated from current DURABILITY II data), $\pi_{pg} = 0.35$ (the *a priori* performance goal), $Z_{1-\alpha} = 1.96$ and $Z_{1-\beta} = 1.28$ gives a sample size of 62. Allowing for approximately 30% of subjects lacking a 3-year follow-up visit, the needed sample size under this approximation for 90% power is a minimum of 89.

An additional sample size requirement is based on the secondary endpoint of freedom from stent fracture at 1 year. In DURABILITY I and DURABILITY II, 1-year stent fracture rates of 8.1% (n=151) and 0.4% (n=287), respectively, were observed. The pooled fracture rate of these two studies is 3.0% (13/438), around which a confidence interval of specified width is desired. The desired precision is 7.2%

(half-width of 3.6%); we therefore find a 95% two-sided normal confidence interval with upper bound $3.0\% + 3.6\% = 6.6\%$, and extract the relevant sample size.

Table 3: Sample Size Freedom from Stent Fracture

Sample Size for Freedom from Stent Fracture			
Sample Size	Count of subjects with event	Event Rate	97.5% upper confidence bound (95% two-sided)
95	3	3.16%	6.67%
96	3	3.13%	6.61%
97	3	3.09%	6.54%
98	3	3.06%	6.47%

From the above table, the required sample size at 1 year is 97 subjects. Considering a 10% rate of attrition, a minimum of 108 subjects are needed, which is larger than the sample size of 89 calculated for the primary endpoint. The enrolled sample size is therefore 108. Please note that multiple stents are allowed in each subject in the study. The stent fracture endpoint will be analyzed on stent level. To be conservative, sample size calculation is performed on subject level. Therefore, more stents than the above assumption may be included in the analysis.

7. Statistical Methods

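### The normal interval behind Protocol Table 10 and SAP Table 3 overstates the fracture precision at 97 subjects: with 3 events the upper limit is about 8.7–8.8%, not 6.6%

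*Protocol*

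**What the plan says.** Protocol section 5.0 (Sample Size and Power) and SAP section 6 add a second sample size requirement, based on freedom from stent fracture at 1 year. The planning rate pools two earlier studies with "1-year stent fracture rates of 8.1% (n=151) and 0.4% (n=287), respectively, were observed", giving 13/438, or 3.0%. The desired full width is 7.2 percentage points, a half-width of 3.6. The Protocol continues: "we therefore find a 95% two-sided normal confidence interval with upper bound" 3.0% + 3.6% = 6.6%.

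Protocol Table 10 (SAP Table 3) holds the count at 3 fractures and lists n = 95 to 98, with bounds of 6.67, 6.61, 6.54 and 6.47%. The column is labelled as a 97.5% upper bound (95% two-sided); no lower limit is printed. The SAP concludes: "From the above table, the required sample size at 1 year is 97 subjects". Allowing 10% attrition gives 108, which exceeds the 89 for the primary endpoint and so becomes the enrolled number.

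Both documents add that fracture will be analysed per stent. In the Protocol's words: "Therefore more stents than the above assumption may be included in the analysis". Fracture will be reported by survival methods. Neither document names the interval method for the reported fracture rate.

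**The concern.** A symmetric normal interval is a weak choice when about 3 events are expected. The binomial distribution is then strongly skewed, and the normal upper limit tends to sit too low. Here that limit is the stated reason for enrolling 108 and not 89. If it is too low, the study has less fracture precision than both documents state. Someone relying on the table would expect 3 fractures in 97 to leave only rates up to about 6.6% compatible with the data, when rates of nearly 9% would still be compatible.

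**Working it through.** **Inputs.** From Protocol section 5.0: x = 3, n = 95 to 98, target upper bound 6.6%, target width 7.2 points, attrition 10%. z = 1.96.

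**1. Reproduce the plan.** The Wald limits are p ± z√(p(1 − p)/n).
- At 3/97, p = 3.093% and the half-width is 1.96 × √(0.03093 × 0.96907/97) = 3.445 points. The interval is -0.35% to 6.54%.
- The upper limits at n = 95, 96, 97 and 98 are 6.67, 6.61, 6.54 and 6.47%. All four match the tables.
- n = 97 is the smallest n with an upper limit at or below 6.6%, and 97/0.9 = 107.8, so 108.

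The plan's derivation reproduces in full. The unprinted lower limit is negative, which is impossible for a rate.

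**2. Does the upper bound behave as a 97.5% bound near 6.6%?** With n = 97, the Wald upper limit is 6.54% at 3 events and 8.08% at 4. If the true rate is 6.6%, the limit therefore falls below the truth exactly when X ≤ 3:

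P(X ≤ 3 | n = 97, p = 0.066) = 0.0013 + 0.0091 + 0.0309 + 0.0692 = 0.1105.

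The miss rate is 11.1% against a nominal 2.5%.

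**3. Two-sided coverage at n = 97.** For each true rate from 2% to 4% in steps of 0.01 point, sum the binomial probabilities of the counts whose interval contains that rate.

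| Method | Mean coverage | Minimum |
|---|---|---|
| Wald | 88% | 80% |
| Jeffreys | 94% | 88% |
| Wilson | 96% | 93.5% |
| Exact (Clopper-Pearson) | 98% | 96.5% |

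Wald coverage is 94.5% at exactly 3.0% but 79.6% at 3.05%, because the Wald upper limit for a single event is 3.04%.

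**4. Other intervals at 3/97.**
- Wilson: (p + z²/2n ± z√(p(1 − p)/n + z²/4n²))/(1 + z²/n) = (0.05073 ± 0.03974)/1.03960, or 1.06–8.70%.
- Exact: the lower limit solves P(X ≥ 3) = 0.025 and the upper solves P(X ≤ 3) = 0.025, giving 0.64–8.77%.
- Jeffreys: 0.88–8.02%.

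| Method | Upper limit (target 6.6%) | Width (target 7.2 points) |
|---|---|---|
| Wald | 6.54% | 6.9 |
| Jeffreys | 8.02% | 7.1 |
| Wilson | 8.70% | 7.6 |
| Exact | 8.77% | 8.1 |

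Wilson and exact miss both targets. Jeffreys meets the width but not the bound.

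**5. Does counting stents repair it?** Protocol section 3.0 says of DURABILITY II "A total of 303 stents were implanted", in 287 subjects. At that ratio, 97 × 303/287 = 102.4 stents. At 3/102 the upper limits are 8.29% (Wilson), 8.36% (exact) and 7.64% (Jeffreys). With 3 events, Wilson and exact reach 6.6% only at 130 units, or 130/97 = 1.34 stents per subject, in a study that intends one stent each. Correlation between stents in one subject would widen the limits further.

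**The case against.** The strongest reply is that nothing is miscalculated. The plan declares a normal interval, and every printed figure follows from it. That stands: a reader might infer an arithmetic error, and the documents do not support that reading. Disclosure does not, however, give the bound the confidence level in its column heading.

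A second reply is that the stated aim is a width, and the width is nearly met. The Wald formula at 3.0% with a 3.6-point half-width needs 1.96² × 0.03 × 0.97/0.036² = 86.3, so 87 evaluable; 97 already includes some margin, and Jeffreys meets 7.2 points. This also stands in part. The width shortfall is 0.4 points with Wilson and 0.9 with exact; the larger gap is in the upper bound.

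Third, the size of the gap depends on the interval chosen, and it would be wrong to call one set valid and the rest invalid. Without censoring, a Kaplan-Meier interval on the log-survival scale has an upper limit of 6.48%, though its lower limit is negative too (-0.41%); arcsine-square-root gives 7.44% and log-log 9.28%. Jeffreys coverage itself drops to 88% in places. The supportable claim is comparative: Wald performs worse on average over the relevant rates than Wilson, exact or Jeffreys.

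Fourth, a reader might infer that the trial is too small or will wrongly rule out fracture rates above 6.6%. The documents support neither. Of the secondary endpoints the Protocol says "No formal statistical hypothesis testing will be performed", no decision rule uses 6.6%, and the primary endpoint needs only 89.

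**Conclusion.** The point holds as an optimistic planning approximation, and it is minor. At 97 evaluable subjects with 3 fractures, the precision to expect is about 1.1–8.7% (Wilson) or 0.6–8.8% (exact), against the plan's 6.6% upper bound and 7.2-point width. The upper limit is understated by about 2 percentage points. The primary hypothesis, its power and its analysis are untouched.

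These figures assume independent subject-level binomial counts with complete 1-year data, as Table 10 does. The planned analysis is per stent and by survival methods, so censoring and clustering will move the actual limits; the documents do not quantify either. The stent-level check assumes the DURABILITY II stents-per-subject ratio.

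**What to change.** Keep N at 108. The Protocol timeline gives "Estimated Date of Last Subject Enrolled: Q1 2015", before version 3.1 of 17 November 2016, so the correction belongs in the stated precision and not in the enrolment.

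1. In Protocol Table 10 and SAP Table 3, replace the normal limits with Wilson or exact limits and print both. For n = 95, 96, 97 and 98 the exact limits are 0.66–8.95, 0.65–8.86, 0.64–8.77 and 0.64–8.69%.
2. Replace 6.6% and 7.2 points with the precision expected at 97 evaluable and 3 fractures: about 1.1–8.7% (Wilson, width 7.6) or 0.6–8.8% (exact, width 8.1).
3. Reword the sentence that derives 97 from the table. With the new limits no printed row meets 6.6%, so it should say that 97 was chosen from a normal approximation and now gives the restated precision.
4. In SAP 7.7, name a non-Wald interval for the reported fracture rate, for example log-log for the Kaplan-Meier estimate, or Wilson or exact for a proportion. This matters most if fractures are as rare as the 0.4% seen in DURABILITY II: at 0/97 the Wald interval collapses to 0–0%, while the exact interval is 0–3.7%.

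The cost is text and table edits in both documents. The stated precision becomes less favourable, and exact limits are somewhat conservative (about 98% coverage over 2–4%); Wilson is narrower and nearer 95%. No extra patients are needed and the primary analysis does not change.

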6.0 RISK/BENEFIT ANALYSIS

The study is designed to minimize risk through observance of strict site and investigator selection criteria, careful subject selection and management, and rigorous adherence to a standardized schedule of post-procedure evaluations.

Potential Benefits

There are no guaranteed benefits from participation in this study; however, it is possible that treatment with the EverFlex stent may improve blood flow through the treated artery. This may result in subjects experiencing fewer or less severe leg symptoms.

Information gained from the conduct of this study may be of benefit to other persons with the same medical condition.

Potential Risks

Risks Associated with Peripheral PTA and Stenting

The risks associated with PTA and stenting of the SFA, including the proximal popliteal artery may include but are not limited to the following.

Table 11: Risks Associated with Peripheral PTA and Stenting

POTENTIAL ADVERSE EVENTS

The potential adverse effects (e.g., complications) that may occur and/or require intervention with the use of this device include, but are not limited to:

 Abrupt or sub-acute closure Allergic reaction to device materials or procedure medications Allergic reaction to Nitinol Amputation Aneurysm Angina Arrhythmia Arterio-venous fistula Artery perforation or rupture Bleeding requiring transfusion Bruising Contrast medium reaction/renal failure Death Device breakage Dissection or intimal flap Edema 	 Infection Inflammation Intraluminal thrombus Myocardial infarction Pain Partial stent deployment Pseudoaneurysm Renal failure requiring dialysis Renal insufficiency (new or worsening) Restenosis Sepsis Shock Stent collapse or fracture Stent migration Stent misplacement
 Amputation Aneurysm Angina Arrhythmia Arterio-venous fistula Artery perforation or rupture Bleeding requiring transfusion Bruising Contrast medium reaction/renal failure Death Device breakage Dissection or intimal flap Edema Embolism Failure to deploy stent Equar 	 Pain Partial stent deployment Pseudoaneurysm Renal failure requiring dialysis Renal insufficiency (new or worsening) Restenosis Sepsis Shock Stent collapse or fracture Stent migration Stent misplacement Stroke Surgical or endovascular intervention
 Gastrointestinal bleeding due to anticoagulation Hematoma Hypertension/hypotension 	 Thrombosis/occlusion of the stent Transient ischemic attack Venous thromboembolism Vessel spasm

As with any device requiring mechanical deployment and retraction, such as the EverFlex device, there exists a risk of mechanical failure of the device resulting in potential surgical intervention to remove the stent or delivery system.

It is expected that the fluoroscopy time of the stenting procedure will be minimally longer (in order to confirm angiographic inclusion and exclusion criteria) than the time required for stenting procedures using other devices and will not pose additional risks to the subject or laboratory personnel.

All of the above could cause prolonged illness, permanent impairment of daily function, or, in rare cases, death. Possible treatments could include, but are not limited to cardiac surgery and vascular surgery.

Extensive reliability engineering testing has been performed on the EverFlex device to mitigate risks to the subject due to product failure. Additionally, studies using the EverFlex device have been conducted to ensure that the system performs as intended without introducing more risks during the index procedure or during follow-up. Risks of the EverFlex stent may be further limited by providing medications such as aspirin or clopidogrel and continuing to monitor subjects following stent implantation.

While some of the potential risks identified have occurred in prior stent implantation studies, and while ev3 believes that the risk for significant injury or death due to the EverFlex device is quite low, these risks have yet to be adequately and fully quantified. Eligibility criteria that exclude subjects who are at higher risk for experiencing an anticipated adverse event have been selected in order to reduce the potential risks to subjects that participate in this study.

Risks Associated with Required Medications

There are also anticipated risks associated with recommended medications.

Subjects should receive anticoagulation and antiplatelet therapy according to the implanting physician's standard of care.

It is recommended that subjects receive aspirin indefinitely for atherosclerotic therapy. The standard risks associated with long-term aspirin therapy as described in the product labeling apply. These risks may include gastrointestinal symptoms such as nausea, vomiting, stomach pain and gastrointestinal bleeding. Other complications such as ringing in the ears, liver toxicity, rash, kidney impairment, vertigo and lightheadedness can also occur.

Subjects also should receive clopidogrel for at least four weeks following their EverFlex stent implantation. The standard risks associated with short-term use of clopidogrel as described in the product labeling apply. The risks of clopidogrel may include chest pain, flulike symptoms, pain, headache, dizziness, upset stomach, bruising and respiratory infection. The major risk of taking a combination of aspirin and clopidogrel for any period of time is possible increase in the risk of a bleeding event.

Risks Associated with Magnetic Resonance Imaging

The use of Magnetic Resonance Imaging (MRI) can induce electrical voltages and currents on the implanted stent, causing heating around the device that may potentially result in tissue damage. Non-clinical testing demonstrates that the EverFlex stent is MR Conditional.

Refer to the Instructions for Use for additional safety information on MRI use.

